## 9.2. Time period and Frequency for collecting AE and SAE information

- At each visit/contact, AEs and SAEs will be collected from the first dose (start of Study Treatment) until 28 days after the last dose of study treatment or until the start of new anti-cancer therapy-whichever occurs first.
- Medical occurrences that begin prior to the start of study treatment but after obtaining informed consent may be recorded on the Medical History/Current Medical Conditions section of the CRF.
- Any SAEs assessed as related to study participation (e.g., protocol-mandated procedures, invasive tests, or change in existing therapy) or related to a GSK product will be recorded from the time a subject consents to participate in the study up to and including any follow-up contact.
- All SAEs will be recorded and reported to GSK within 24 hours, as indicated in [Appendix 6](#).
- Investigators are not obligated to actively seek AEs or SAEs in former study subjects. However, if the investigator learns of any SAE, including a death, at any time after a subject has been discharged from the study, and he/she considers the event reasonably related to the study treatment or study participation, the investigator must promptly notify GSK.

NOTE: The method of recording, evaluating and assessing causality of AEs and SAEs plus procedures for completing and transmitting SAE reports to GSK are provided in [Appendix 6](#)

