### **5.4. Withdrawal/Stopping Criteria**

Subjects will receive study treatment until disease progression, death or unacceptable adverse event, including meeting stopping criteria for liver chemistry, hematologic/non-hematologic toxicity, QTc prolongation, raised Troponin level as defined in Section 14.7.1 or left ventricular ejection fraction (LVEF)/valvular dysfunction as defined in Section 5.4.1 through Section 5.4.5. After disease progression, subjects may be allowed to continue treatment with study drug if the Investigator strongly believes, and the GSK Medical Monitor concurs, that the subject could continue to receive benefit (for example in cases of an isolated new lesion, with the majority of the disease still under control).

In addition study treatment may be permanently discontinued for any of the following reasons:

- deviation(s) from the protocol
- request of the subject or proxy
- investigator's discretion
- subject is lost to follow-up
- study is closed or terminated.

The primary reason study treatment was permanently discontinued must be documented in the subject's medical records and electronic case report form (eCRF).

If the subject voluntarily discontinues from treatment due to toxicity, 'adverse event' will be recorded as the primary reason for permanent discontinuation on the eCRF.

Once a subject has permanently discontinued from study treatment, the subject will not be allowed to be retreated.

All subjects who discontinue from study treatment will have safety assessments at the time of discontinuation and during post study treatment follow-up as specified in Time and Events Tables (see Section 8.1).

All subjects who permanently discontinue study treatment for any reason will be followed for survival and new anti-cancer therapy (including radiotherapy) every 6 months until death, termination of the study by the sponsor, or until the subject has been followed for 2 years. Disease assessment will be collected for subjects who discontinue study medication due to any reason other than progression. If subjects are unable or unwilling to attend clinic visits during follow-up, contact to assess survival may be made via another form of communication (e.g., telephone, email, etc.).

The following actions must be taken in relation to a subject who fails to attend the clinic for a required study visit:

- The site must attempt to contact the subject and re-schedule the missed visit as soon as possible.

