#### 7.1.2.2. Prohibited Non-Drug Therapies

Non-drug anti-cancer therapies (e.g., radiation therapy, surgery, and/or tumor embolization) will not be permitted from the screening visit through the post-study follow-up visit.

**NOTE:** Subjects may receive focal palliative radiation treatment during this study. Any proposed radiation therapy must be approved by the investigator and the GSK Medical Monitor prior to initiation.

Subjects will abstain from using herbal preparations/medications throughout the study until the final study visit.

Herbal products include, but are not limited to: St. John's Wort, kava, ephedra (ma huang), ginkgo biloba, dehydroepiandrosterone (DHEA), yohimbe, saw palmetto, ginseng.

The investigator should contact a GSK Medical Monitor before initiating treatment with any herbal preparation including marijuana.

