8.1. Time and Events Tables

Table 7 Time and Events

Assessments	Notes	S C R	Refer to Section 8.4.2 for visit windows.																				E O T				
			Week 1							Week 2							W3		W4		W5	W7		W9	q4W	q8W	
			D 1	D 2	D 3	D 4	D 5	D 6	D 7	D 1	D 2	D 3	D 4	D 5	D 6	D 7	D 1	D 4	D 1	D 4	D 1	D 1		D 1	D 1	D 1	
Informed consent	Unless otherwise noted, screening assessments to be completed within 14 days of first dose.	X																									
Demography		X																									
Medical history		X																									
Disease characteristics		X																									
Cardiology evaluation		X																									
Prior therapy		X																									
Register subject		X																									
TREATMENT PHASE																											
Study Drug																											
Administer study drug	Administer about same time of day. No food or antacids 1h before and 2h after.		X		X	X	X				X	X	X	X	X												Daily
Review subject diary	Diary not required when dosed in clinic.									X							X	X		X	X	X	X				
Safety																											
Pregnancy test/ testosterone	Females: serum pregnancy test within 7 days of first dose; urine or serum test thereafter. Males: complete and free testosterone at SCR; free testosterone thereafter.	X	X																		X			X	X		X
Physical exam		X	X							X							X	X		X	X	X	X			X	
ECOG PS		X	X							X							X	X		X	X	X	X			X	

Assessments	Notes	S C R	Refer to Section 8.4.2 for visit windows.																				E O T						
			Week 1							Week 2							W3		W4		W5	W7		W9	q4W	q8W			
			D1	D2	D3	D4	D5	D6	D7	D1	D2	D3	D4	D5	D6	D7	D1	D4	D1	D4	D1	D1		D1	D1	D1			
Vital Signs	SBP, DBP, heart rate, respiratory rate, temp, O2 saturation	X	X	X				X		X					X		X		X		X		X	X	X	X		X	
Pain (using Wong-Baker Faces Pain Rating scale)		X	X	X				X		X					X		X		X		X		X	X	X	X		X	
Weight and height	Height at SCR only	X	X							X							X		X		X		X	X	X	X		X	
Chest x-ray		X																											
Pulmonary function tests (spirometry, Diffusing capacity of the lungs for carbon monoxide [DLCO], and room air O2 saturation at rest via pulse oximetry)	All patients will have PFTs at baseline; afterwards as clinically indicated (e.g., in patients with severe Chronic Obstructive Pulmonary Disease [COPD], history of pneumonitis, alveolar haemorrhage and chest radiation etc)	X																											
Adverse events		continuous from signing of informed consent																											

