**Table 11 Clinical Laboratory Tests**

Serum Chemistry			
Blood urea nitrogen	Magnesium	aspartate aminotransferase	Total and direct bilirubin
Sodium	Potassium		Uric acid
Creatinine	Chloride	alanine aminotransferase	Albumin
Fasting Glucose	Total carbon dioxide	alkaline phosphatase	Total protein
Creatine phosphokinase	Ionized calcium	gamma-glutamyltransferase	Total calcium
Hematology			
Platelet count	Automated White Blood Cell		
Red blood cell count	Differential:		
White blood cell count (absolute)	Neutrophils (absolute)		
Hemoglobin	Lymphocytes (absolute)		
	Monocytes (absolute)		
	Eosinophils (absolute)		
	Basophils (absolute)		
Routine Urinalysis			
Specific gravity			
pH, glucose, protein, blood, and ketones by dipstick			
Microscopic examination (if blood or protein is abnormal)			
Other Tests			
Coagulation tests (prothrombin time, partial thromboplastin time, international normalized ratio, and fibrinogen)			
Pancreatic markers (amylase and lipase)			
Fasting_Lipid panel (triglycerides and total cholesterol, low density lipoprotein [LDL], high density lipoprotein [HDL])			
C-Peptide			
Troponin (I or T at local laboratory, Troponin T at central laboratory)			
Insulin			
Hemoglobin A1C			
1,5 -Anhydroglucitol (1,5 AG)			
NT-proBNP			
Thyroid-stimulating hormone (TSH)			
Free Thyroxine 3 (Free T3)			
Free Thyroxine 4 (Free T4)			
Creatine kinase (CK)			
Creatine Kinase-MB isoenzyme (CK-MB)			
Testosterone for males (free and complete testosterone at prior to first dose, free testosterone after first dose)			
Pregnancy test for females (serum at screening, Urine or serum post dose)			
Cytokine samples			

Subjects should be instructed to fast (no food and only water allowed) for 10 hours prior to any fasting laboratory assessments (e.g., fasting glucose, fasting lipid panel, etc.).

All laboratory results that are considered by the investigator clinically significantly abnormal during participation in the study or within 28 days after the last dose of study treatment should be recorded on the eCRF as AEs. In addition, these clinically significant abnormal laboratory results should be followed until the abnormality resolves or is determined to be stable. If such values do not return to normal within a period judged reasonable by the investigator, the etiology should be identified and the sponsor notified.

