**Time to Event and Overall Response:**

Start dates for follow-up anticancer therapy, radiotherapy (where applicable), and surgical procedures (where applicable) will be temporarily imputed in order to define event and censoring rules for progression-free survival, response rate, or duration of response (i.e. start date for new anticancer therapy). Dates will only be imputed when a month and year are available but the day is missing. The imputed date(s) will not be stored on the anticancer therapy, radiotherapy, or surgical procedure datasets. The following rules will be used to impute the date when partial start dates are present on anticancer therapy radiotherapy, and/or surgical procedures dataset[s]:

Dataset	Date	Missing Element	Rule
Anticancer Therapy  Where applicable: Radiotherapy  Surgical Procedures	Start Date	day, month, and year	
 
No Imputation for completely missing dates
 

Dataset	Date	Missing Element	Rule
		day, month	
 
No imputation for missing day and month (note the eCRF should only allow for missing day)
 

		day	
 
If partial date falls in the same month as the last dose of study treatment, then assign to earlier of (date of last dose of study treatment+1, last day of month).
 
If partial date falls in the same month as the subject's last assessment and the subject's last assessment is PD, then assign to earlier of (date of PD+1, last day of month).
 
If both rules above apply, then assign to latest of the 2 dates
 
Otherwise, impute missing day to the first of the month.
 

	End Date		
 
No imputation for partial end dates will be performed
 

The date of new anticancer therapy is derived as the earliest date of new anticancer therapy (e.g., chemotherapy), radiotherapy (where applicable), or cancer related surgical procedure (where applicable) and will include imputed dates.

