- If anticancer therapy is started without documented disease progression or is started prior to documented disease progression, then PFS will be censored at the date of the last adequate assessment that is no later than the date of initiation of anticancer therapy (i.e. if an assessment occurs on the same day as the start of new anticancer therapy the assessment will be used - as it will be assumed the assessment occurred prior to the administration of new anticancer therapy). The date of response at the last adequate assessment will be used as the censoring value.

A summary of the assignments for progression and censoring dates for PFS are specified in the following table.

Table 1. Assignments for Progression and Censoring Dates for PFS Analysis

Situation	Date of Event (Progression/Death) or Censoring	Outcome Event (Progression/Death) Or Censored
No ( or inadequate ) baseline tumor assessments and the subject has not died (if the subject has died follow the rules for death indicated at the bottom of the table)	Start Date of Treatment	Censored
No post-baseline assessments and the subject has not died (if the subject has died follow the rules for death indicated at the bottom of the table)	Start Date of Treatment	Censored
Progression documented between scheduled visits	Date of assessment of progression 	Event
No progression ( or death ) and no initiation of new anti-cancer therapy	Date of last ‘adequate’ assessment of response 	Censored
Received subsequent anti-cancer therapy prior to the date of documented events	Date of last ‘adequate’ assessment of response  ( prior to starting initiation of therapy )	Censored
Received subsequent anti-cancer therapy prior to any adequate assessment	Start Date of Treatment	Censored
Received subsequent anti-cancer therapy and no progression ( or death )	Date of last ‘adequate’ assessment of response  ( prior to starting initiation of therapy )	Censored
Death or progression after more than one missed visit	Date of last ‘adequate’ assessment of response  ( prior to missed assessments )	Censored
Death	Date of Death	Event

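### Protocol 9.2 ends general AE/SAE collection at new anti-cancer therapy without requiring that study drug has stopped, although palliative radiotherapy and surgery are permitted during the study

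*Protocol*

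**What the plan says.** **AE collection.** The first bullet of Protocol 9.2 runs general AE and SAE collection from first dose "until 28 days after the last dose of study treatment or until the start of new anti-cancer therapy-whichever occurs first". A later bullet of the same section keeps one class open: SAEs related to study participation or to a sponsor product "will be recorded from the time a subject consents to participate in the study up to and including any follow-up contact". Two other places describe AE recording without a stop at new therapy. Table 7 has adverse events "continuous from signing of informed consent". Section 8.3.9, under Table 11, says that clinically significant laboratory abnormalities "during participation in the study or within 28 days after the last dose of study treatment should be recorded on the eCRF as AEs".

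**Palliative treatment.** Section 7.1.2.1 lists radiation and surgery among the other anti-cancer therapies barred during treatment, then adds a note that palliative radiation or surgery may be allowed after discussion with the medical monitor. Section 7.1.2.2 lists radiation and surgery as non-drug anti-cancer therapies, then notes: "Subjects may receive focal palliative radiation treatment during this study". Section 5.4 refers to "new anti-cancer therapy (including radiotherapy"), in describing follow-up after permanent discontinuation.

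**Efficacy.** SAP 8.2.5 states: "The date of new anticancer therapy is derived as the earliest date of new anticancer therapy (e.g., chemotherapy), radiotherapy (where applicable"), and also counts cancer-related surgery where applicable. SAP Section 10 states: "If anticancer therapy is started without documented disease progression or is started prior to documented disease progression, then PFS will be censored". The censoring date is that of the most recent adequate scan up to that point. Appendix 8 of the protocol deals with irradiated lesions only when baseline target lesions are chosen.

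**The concern.** AEs and SAEs are the core of the primary endpoint, and the reason to collect them is exposure to study drug. A cut-off at new anti-cancer therapy makes sense after the drug has been stopped, because later events are then hard to attribute. It makes little sense while dosing continues. Section 9.2 takes whichever of two dates comes first and does not tie the new-therapy date to the end of dosing, so it can close the window on a subject who is still exposed. Section 5.4 also lets some subjects stay on drug after progression, which adds on-drug time in which local palliative treatment could be given.

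At stake are non-serious AEs, including any non-serious event that would qualify as a DLT, and SAEs judged unrelated. Sites also face three instructions that cannot all be followed.

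A second, smaller gap concerns efficacy. The plan does not say whether permitted on-treatment palliative radiotherapy triggers PFS censoring, or how a target lesion irradiated on study should be scored.

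**Working it through.** The plan gives no figure to reproduce on this point. The check is a comparison of the text, followed by two illustrations on assumed values.

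**Step 1: is permitted palliative treatment inside the class of anti-cancer therapy?** In both 7.1.2.1 and 7.1.2.2 the permission is an exception to a prohibition on a list that contains radiation and surgery. It does not reclassify them. No section exempts palliative use from the term, and none states outright that it is new anti-cancer therapy. The classification is therefore the natural inference, not a definition.

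**Step 2: when does AE collection stop for a subject who is irradiated but still dosed?**

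| Source | Stop rule | Result |
|---|---|---|
| 9.2, first bullet | earlier of last dose + 28 days and new therapy | stops at radiotherapy |
| 9.2, related SAEs | any follow-up contact | continues |
| Table 7 | none stated | continues |
| 8.3.9, laboratory AEs | last dose + 28 days | continues |
| 9.1.2, safety results leading to a dose change or discontinuation | none stated | an AE or SAE is to be recorded |

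On the literal reading, the loss is non-serious AEs and unrelated SAEs, less whatever 8.3.9 and 9.1.2 bring back. Table 7 and 9.2 also differ on the start: consent in one, first dose in the other.

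**Step 3: size for one affected subject (assumed start day).** The DLT window is 4 weeks, or 28 days (Section 4.2.4). If radiotherapy starts on Day d, the days of that window without general collection are 28 − d + 1.

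- d = 2: 27 days
- d = 15: 14 days, half of the window
- d = 28: 1 day

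All later dosing, and the 28 days after the last dose, would also lack general collection.

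**Step 4: target lesion irradiated on study (assumed lesions).** Appendix 8 defines PR as a fall of at least 30% in the sum of target diameters, to be confirmed at 28 days or more. Take n equal targets, with one irradiated and shrinking by a fraction s and the others unchanged. The fall in the sum is s/n.

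- n = 1: PR needs s ≥ 30%
- n = 2: s ≥ 60%. For example, 40 + 40 = 80 mm becomes 16 + 40 = 56 mm, and (80 − 56)/80 = 30%
- n = 3: s ≥ 90%
- n = 4 or 5: not reachable, since complete disappearance gives at most 25% or 20%

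So PR from local treatment alone is possible only with few target lesions. Appendix 8 runs best overall response to progression without a cut at new therapy. SAP 8.2.5 says that the new-therapy date serves response-rate rules, but the SAP writes none.

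**The case against.** The strongest case on the other side is that the classification is only inferred and that the surrounding text points to treatment given after study drug. The radiotherapy wording in 5.4 concerns subjects who have permanently discontinued. The SAP speaks of follow-up and subsequent therapy, and its rule for a partial start date can assign the day after the last dose, which presumes that dosing has ended. On that reading, on-study palliative radiotherapy may lie outside the PFS censoring rule. This stands: on PFS the documents are silent, not wrong. It does not rescue 9.2, where the trigger is not tied to the end of dosing.

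A reader might infer that all later AEs and any later progression are lost for such a subject. The documents do not support that. Related SAEs stay open under 9.2, and Table 7, 8.3.9 and 9.1.2 each point to further recording. SAP 8.2.9 keeps every assessment in the listings, so later progression would still appear in Listings 47 to 50; only the derived PFS listing could show censoring.

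A reader might also infer a lengthened PFS curve, an inflated response rate, or that one of 5 subjects, 20% of the data, is affected. The SAP produces listings only and does not calculate ORR, although it notes that responses can be counted from the listings. No document says that any subject was irradiated on study.

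**Conclusion.** The point holds for AE collection. Section 9.2 as written can end general AE/SAE collection while a subject is still on study drug, and it disagrees with Table 7 and 8.3.9. The affected events are non-serious AEs and unrelated SAEs. The conclusion rests on two things: reading permitted palliative radiotherapy or surgery as new anti-cancer therapy, which the text implies but does not state, and a site applying 9.2 literally.

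The likely effect on the final report is small, given 5 enrolled subjects and listings only, but the ambiguity touches the primary endpoint and is cheap to remove.

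The efficacy gap is secondary. Whether permitted palliative treatment should censor PFS is a legitimate choice either way; the fault is that the choice is not stated. The same applies to a target lesion irradiated on study.

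**What to change.** **Protocol 9.2.** Apply the early stop at new anti-cancer therapy only after permanent discontinuation of study drug, so that general AE/SAE collection continues for as long as dosing does. Bring 9.2, Table 7 and 8.3.9 to one start and one stop rule. This costs one line and two cross-checks. It changes only data collection, not treatment. Since the SAP reports that the study has ended, the report should also say which rule the sites followed for any subject given palliative treatment while on drug.

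**SAP and Appendix 8.** State whether permitted on-treatment palliative radiotherapy or surgery sets the new-therapy date for PFS, and how a target lesion irradiated on study is treated in the response assessment. Flag any such subject in Listings 47, 48 and 51. This costs two sentences and a flag.

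A PFS exemption is not required. Nor is a rule making the irradiated target not evaluable recommended as a companion to one. Under Table 13, a target response of not evaluable without progression gives an overall response of not evaluable, and the SAP counts only CR, PR or SD as adequate. Later scans without progression would then not count, and PFS would fall back to the last scan before radiotherapy. Progression or death more than 119 days (16 × 7 + 7) after that scan would be censored as well. The rule would largely bring back the censoring that the exemption was meant to avoid.

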### 9.2.1. Method of Detecting AEs and SAEs

Care will be taken not to introduce bias when detecting AEs and/or SAEs. Open-ended and non-leading verbal questioning of the subject is the preferred method to inquire about AE occurrence. Appropriate questions include:

- "How are you feeling?"

- “Have you had any (other) medical problems since your last visit/contact?”
- “Have you taken any new medicines, other than those provided in this study, since your last visit/contact?”

### **9.2.2. Follow-up of AEs and SAEs**

After the initial AE/SAE report, the investigator is required to proactively follow each subject at subsequent visits/contacts. All SAEs, and non-serious AEs of special interest (as defined in Section 4.6.1) will be followed until resolution, until the condition stabilizes, until the event is otherwise explained, or until the subject is lost to follow-up (as defined in Section 5.4). Further information on follow-up procedures is given in [Appendix 6](#).

